At the pre-operative clinic appointment, patients will be recruited into the study. Informed consent will be obtained from the patient by the study doctor. The nature of the experiment will be explained, specifically that the patient agrees to be randomized to receive a block prior to the operation or to receive the joint injection at the conclusion of the surgery as an adjunct to general anesthesia. If the patient agrees to enter into the study, the patient will be randomized by use of a computer generated randomization program at the time of enrollment in the clinic. Currently, the standard of care at the Steadman Hawkins Clinic of the Carolinas is to offer surgical patients a block as an analgesic option. Fl blocks are not ordered by the doctor without a request by the patient. If patients do not receive a Fl block, they will receive a local anesthetic intraoperatively by the surgeon at the close of the procedure, which is also currently the standard of care for hip surgery.

On the day of surgery, all patients will receive multimodal analgesia with an oral preoperative cocktail consisting of acetaminophen 15mg/kg up to a maximum of 1000mg, celebrex 400mg, lyric 75mg, and oxycontin 10mg unless they are allergic to any of the components. Both block (B) and non-block (NB) patients will receive pre-operative midazolam 1-5 mg as needed for procedural sedation (B) or pre-operative anxiety (NB) respectively.

Patients to be blocked will receive not less than 50 ml and up to 60 mL of 0.35% ropivacaine at a dose of 3 mg/kg (with adjuvants of 100 mcg clonidine [per 60 mL] and epinephrine 1:400,000) placed using a 17 gauge 3.2" B-Braun Tuohy needle under ultrasound guidance using a SonoSite S-Nerve machine with a 15-10 MHz 38 mm probe using a caudad to cephalad in-plane approach. (A 70kg patient would receive all 60 mL of the block solution and 210mg of ropivacaine total). The blocks will be placed exclusively by a selected group of anesthesiologists, who have been trained in the technique.

Patients who are randomized to no-block will receive a single injection of Noropin in the joint space.

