General anesthesia will be conducted in a standard fashion for all patients. General anesthesia with an endotracheal tube will be induced with IV fentanyl 2 mcg/kg, lidocaine 50mg, propofol 2 mg/kg, and rocuronium 0.6 mg/kg unless another plan is chosen at the discretion of the attending anesthesiologist. Maintenance of anesthesia will be done with O2:air FIO2 50%, isoflurane end-tidal concentration of 0.7-1.4%, and tidal volumes of 7-10 mL/kg with a respiratory rate to maintain an end-tidal carbon dioxide concentration of 30-40 mmHg. Fentanyl will be given in 25-50 mcg increments for HR or BP greater than 20% over baseline. No long acting intra-operative opioids will be administered and only fentanyl will be used. Ephedrine in 5-10 mg increments or neosynephrine in 80-160 mcg increments will be used to treat hypotension at the anesthesiologist's discretion. A minimum of 20mL/kg of IV crystalloid will be administered during the surgery. Ondansetron 4 mg IV will be administered to all patients approximately 30 minutes prior to emergence for PONV prophylaxis.

Post-operatively in the recovery room, hydromorphone will be used as a first line opioid for pain given in 0.2-0.5 mg increments to an initial maximum of 4 mg. Nausea will be treated in a stepwise fashion with promethazine 6.25 mg IV as a first line agent. Second line will be a repeat dose of promethazine 15 minutes after the first dose, followed by diphenhydramine 6.25 mg IV 15 minutes later PRN. Pain scores will be recorded initially upon arrival to the PACU and thereafter until the patient is discharged from the PACU. All episodes of nausea and vomiting will be tallied. Total recovery time in the PACU will be recorded. If a patient is otherwise ready for discharge but remains in the PACU due to a non-medical issue (i.e. bed hold), the time at which the patient could have otherwise been discharged will be

recorded as the PACU end time for the purposes of the study. Any unplanned admissions will be noted. All opioids administered intraoperatively and in the PACU will be recorded and converted to morphine equivalents.

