Patients will be followed in the study surgeon's clinic office per his standard protocol at 2 weeks, 6 weeks, and 3 months post-operatively. Pain scores will be evaluated at this time. Clinical outcome measures and range of motion of the patients' hips will be collected at this time as well. Any adverse reaction from the block will be noted and recorded at all times from the administration of the block and at each clinic follow up. Any signs or symptoms of numbness in the distribution of the fascia iliaca block will be noted.

- Primary endpoint: Quantify the difference in pain in patients who have received a pre-operative FI block versus those receiving no block.
  - Secondary endpoint: Quantify the difference in opioid consumption in patients who have received a pre-operative FI block versus those receiving no block.
  - Tertiary endpoints: Assess differences in episodes of PONV, time in PACU, and proportion of unplanned admissions
- Risks / benefit
  - Risks associated with FI blocks are the following:

Overall the procedure has a very low risk profile. The location of the injection means the risk of intravascular injection, local anaesthetic toxicity, and mechanical nerve damage is extremely low.

Good aseptic technique will minimize the risk of infection. The injection of a large volume of local anaesthetic ensures good spread and reduces the risk of failure. The risk of local anaesthetic toxicity is highest within the first 15 minutes after injection, which makes close monitoring mandatory.
  - The potential benefit is improvement in pain control and opioid consumption in FI patients. The knowledge gained from this study will also be used in future patients with this condition.

- **Statistical Analysis**

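### Below 58.3 kg, the 50 mL block minimum at 0.35% exceeds the stated 3 mg/kg ropivacaine dose, and eligibility sets no minimum weight

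*Combined protocol and SAP*

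**What the plan says.** The Study procedure text under Study Methodology specifies the block as "not less than 50 ml and up to 60 mL of 0.35% ropivacaine at a dose of 3 mg/kg", with clonidine 100 mcg per 60 mL and epinephrine 1:400,000 as adjuvants. One worked example follows: "A 70kg patient would receive all 60 mL of the block solution and 210mg of ropivacaine total". No example or rule is given for a lighter patient.

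The eligibility lists in the same section admit ages 18 to 65 and ASA classes 1 to 3. The only body-size criterion excludes BMI above 40. There is no minimum weight or BMI, and excluding patients with a contraindication to regional anesthesia is not a weight limit.

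Two further statements bear on the choice between volume and dose. The Risks / benefit text gives a reason for volume: "The injection of a large volume of local anaesthetic ensures good spread and reduces the risk of failure". It describes toxicity in these terms: "The location of the injection means the risk of intravascular injection, local anaesthetic toxicity, and mechanical nerve damage is extremely low". No reason is given anywhere for the figure of 3 mg/kg.

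**The concern.** The block sentence fixes concentration, a volume range and a dose per kilogram together. Once the weight is known, any two of these determine the third, so they agree only over a limited range of weights. Below that range, nothing says whether the dose or the minimum volume gives way.

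The block is the experimental intervention, so its dose should be reproducible from the protocol. As written, two anesthesiologists reading the same sentence could give a 50 kg patient 175 mg in 50 mL or 150 mg in 42.9 mL, and either choice would depart from part of the instruction. What is at stake is a clear drug-dose instruction and consistent delivery of the intervention in lighter patients.

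**Working it through.** **Inputs**, all from the Study procedure text: concentration 0.35%, which is 3.5 mg/mL; volume 50 to 60 mL; dose 3 mg/kg.

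**Formulas**
- Dose (mg) = 3 × weight (kg)
- Volume (mL) = dose / 3.5 = 0.857 × weight
- Weight at which a given volume delivers exactly 3 mg/kg = volume × 3.5 / 3

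**Reproducing the protocol's example.** At 70 kg: 3 × 70 = 210 mg, and 210 / 3.5 = 60 mL. Both figures match, so this is how the protocol itself calculates.

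**Range of weights where all three figures hold**
- Lower end: 50 × 3.5 = 175 mg; 175 / 3 = 58.3 kg
- Upper end: 60 × 3.5 = 210 mg; 210 / 3 = 70 kg
- Width: 70 − 58.3 = 11.7 kg

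Inside this band the instruction is consistent: 51.4 mL at 60 kg, 55.7 mL at 65 kg and 60 mL at 70 kg.

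**Below the band.** The documents give no weight distribution, so these weights are illustrative.

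| Weight | 3 mg/kg dose | Volume needed at 0.35% | mg/kg if 50 mL is given | Excess over 3 mg/kg | Concentration for 3 mg/kg in 50 mL |
|---|---|---|---|---|---|
| 55 kg | 165 mg | 165/3.5 = 47.1 mL | 175/55 = 3.18 | 10 mg (10/165 = 6%) | 165/50 = 3.3 mg/mL (0.33%) |
| 50 kg | 150 mg | 150/3.5 = 42.9 mL | 175/50 = 3.50 | 25 mg (25/150 = 17%) | 150/50 = 3.0 mg/mL (0.30%) |

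The excess is zero at 58.3 kg and grows as weight falls.

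**Are such weights plausible?** At illustrative heights, 58.3 kg is a BMI of 58.3/1.60² = 22.8 at 1.60 m and 58.3/1.65² = 21.4 at 1.65 m. Both are well under the exclusion threshold of 40, and consecutive patients are to be enrolled.

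**Does other text resolve it?**
- Reading 3 mg/kg as a ceiling does not help, because the mandatory minimum volume then breaches the ceiling.
- Reading it as a target does not help, because 50 mL overshoots it.
- Dilution is not available, because the concentration is fixed at 0.35%.
- The clause "unless another plan is chosen at the discretion of the attending anesthesiologist" belongs to the induction of general anesthesia. The other grant of discretion there concerns the treatment of hypotension. Neither covers the block.

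**The case against.** The strongest counter-argument concerns consequence. No endpoint, sample size or analysis depends on this sentence. The discrepancy is 10 mg at 55 kg and 25 mg at 50 kg, and the documents do not show that such doses are harmful. Safeguards are in place: "The blocks will be placed exclusively by a selected group of anesthesiologists, who have been trained in the technique"; "The risk of local anaesthetic toxicity is highest within the first 15 minutes after injection, which makes close monitoring mandatory"; and "Any adverse reaction from the block will be noted and recorded at all times from the administration of the block". All of this stands. It limits what could follow from the conflict, but it does not tell the anesthesiologist which figure to follow.

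A second argument is that the 70 kg example, and clonidine being specified per 60 mL, suggest a 60 mL preparation from which a weight-based amount is drawn. In practice a lighter patient would then probably receive less solution. That is a reasonable inference and makes divergent practice less likely. But the example sits at the upper volume limit and does not cancel an explicit minimum.

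A third argument is that the underlying gap is wider, because the sentence never says whether 3 mg/kg is a target or a maximum. If it is a target, 60 mL also falls short above 70 kg (210/80 = 2.63 mg/kg at 80 kg). That is fair. However, the 60 mL figure can reasonably be read as a cap, so no error is claimed at that end. Below 58.3 kg neither reading works.

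**Conclusion.** The concern holds. At 0.35%, the 50 mL minimum and the 3 mg/kg dose cannot both be met in a patient weighing less than 58.3 kg, and the eligibility criteria allow such patients to enroll. The threshold follows directly from the protocol's own figures and needs no outside assumption.

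The illustrative excess is 6% at 55 kg and 17% at 50 kg if the volume is held. If the dose is held, the shortfall from the minimum is 50 − 47.1 = 2.9 mL and 50 − 42.9 = 7.1 mL. The share of patients affected cannot be estimated from the documents. This is a conflict in the dosing specification: the worked example is correct, no toxicity is asserted, and no bias in the treatment comparison is claimed. It should be fixed because it is a drug-dose instruction that cannot be followed as written, and the repair is small.

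**What to change.** Amend the block sentence so that it can be followed at every eligible weight. The clinical team should choose between two options, since the protocol gives a rationale for volume but none for 3 mg/kg.

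**Option A (simplest).** Specify ropivacaine 0.35% at 3 mg/kg (0.857 mL/kg), to a maximum of 60 mL (210 mg), and delete the 50 mL minimum. The weight-based volumes from 58.3 to 70 kg are unchanged, because 0.857 mL/kg already gives at least 50 mL from 58.3 kg upward. It also makes explicit that 60 mL is a cap above 70 kg. The cost is a smaller volume in the lightest patients (42.9 mL instead of 50 mL at 50 kg) and less clonidine. At 100 mcg per 60 mL they would receive 78.6 mcg at 55 kg and 71.4 mcg at 50 kg, against 83.3 mcg in 50 mL.

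**Option B (if 50 mL is wanted for spread).** Below 58.3 kg, keep 50 mL and dilute so that total ropivacaine stays at 3 mg/kg: 0.33% at 55 kg and 0.30% at 50 kg. The cost is a weaker solution and a weight-specific preparation. The text must also say how the adjuvants are handled. If the ready-mixed solution is diluted, a 50 kg patient receives 42.9 mL made up to 50 mL, which carries 71.4 mcg of clonidine and epinephrine weaker than 1:400,000. Keeping the adjuvant concentrations constant means preparing them separately.

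Either option is a one-sentence protocol amendment, with a short addition on adjuvants under Option B. Neither changes the sample size or the analysis.

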## Study Methodology

- Study Description

- Design: Randomized controlled trial
- Blinding:
  - Blinded: Data analyst
  - Unblinded: patient, surgeon and anesthesiologist
- Location: Greenville Health System (Patewood Outpatient Hospital and Hillcrest Memorial Hospital)
- Sample size: Sample size estimates are based on the assumptions of a large clinical effect size (>.40) seen at 5 follow up points for the primary outcome measure of pain. Using a fixed effects, special, main and interactions, analysis of variance testing (ANOVA) with a power of 0.80 and an alpha of 0.05, we estimate the need for 86 subjects to achieve statistical significance. To account for loss of follow up, we will target 10% more subjects, thus 95 total participants.
- **Study population**
  - Subjects
    - Recruitment: Consecutive patients undergoing hip arthroscopy will be enrolled in the study
    - Inclusion criteria:
      - Scheduled for outpatient hip arthroscopy by [name]
      - ASA 1-3
      - Ages 18-65
    - Exclusion criteria:
      - Prior surgery on ipsilateral hip
      - ASA 4-6
      - Chronic narcotic usage over 6 months or more than the equivalent of 20mg of morphine per day
      - Current or prior placement of a spinal cord stimulator or intrathecal pump for pain control purposes
      - Allergy to amide local anesthetics
      - Contraindication to regional anesthesia
      - BMI > 40
      - Females who are pregnant or plan to get pregnant during the course of the study

- **Study procedure**

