The study incorporates four dedicated follow up points beyond baseline: a) perioperative (1 to 5 days), b) 2 weeks, c) 6 weeks, and d) 3 months. The primary outcome measure (pain) will be analyzed using a fixed effects, special, main and interactions, analysis of variance testing (ANOVA). Opioid consumption will be analyzed using a Pearson chi square or parametric equivalent (depending on final coding). Tertiary end points will be captured using an ANOVA for continuous measures (once tests of normality are completed), or Kruskal Wallis, whereas re-admission rates will be analyzed using a Pearson Chi-square. A p value of 0.05 will be considered statistically significant for all findings. Intention to treat and last value carried forward will be integrated for all analyses.

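### Hospital balance is left to chance, and the plan does not say that the same anesthesiologists care for both arms

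*Combined protocol and SAP*

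**What the plan says.** All places are in the combined protocol and SAP, under Study Methodology.

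- **Sites.** The Location item lists two hospitals of one health system: "Patewood Outpatient Hospital and Hillcrest Memorial Hospital". The expected split of patients is not given.
- **Randomisation.** Study procedure says that "the patient will be randomized by use of a computer generated randomization program at the time of enrollment in the clinic". It states no stratification, blocking or allocation ratio.
- **Analysis.** Statistical Analysis says: "The primary outcome measure (pain) will be analyzed using a fixed effects, special, main and interactions, analysis of variance testing (ANOVA"). The factors are not listed. For the other outcomes, "Tertiary end points will be captured using an ANOVA for continuous measures", with a rank test as the alternative and chi-square tests for opioid consumption (or a parametric equivalent) and for admission rates. No hospital or anesthesiologist term is named for any endpoint.
- **Who does what.** For the block arm, "The blocks will be placed exclusively by a selected group of anesthesiologists, who have been trained in the technique". For the other arm, "Patients who are randomized to no-block will receive a single injection of Noropin in the joint space"; Study procedure has the surgeon give it at the end of the operation. Nothing says who conducts the general anesthetic in either arm.
- **Discretion and blinding.** Induction follows a set regimen "unless another plan is chosen at the discretion of the attending anesthesiologist". Under Blinding, only the data analyst is blinded.

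**The concern.** There are two separate issues.

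**Hospital.** Recovery-room practice and the threshold for keeping a patient overnight may differ between hospitals. PACU time and unplanned admission are endpoints, and no admission criteria are given. If hospital is neither a stratum nor a model term, chance imbalance between arms moves the estimate, and the between-hospital variance stays in the error term. Both are avoidable.

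**Anesthesiologist.** Randomising patients does not balance staffing that is decided afterwards. Allocation is fixed at the clinic visit and is not concealed from the anesthesiologist, so it can be known when a case is staffed. A block case needs access to the selected group; a no-block case does not. If the group also conducts the anesthetic, and does so more often in the block arm, its habits in all other care travel with the arm. The most exposed outcome is intraoperative opioid, which counts towards recorded opioid consumption. A bias of this kind would not shrink with more patients.

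**Working it through.** **1. The plan's own figure.** The inputs, from the Sample size item, are effect size 0.40 (read as Cohen's f), alpha 0.05 and power 0.80. With a noncentral F test, noncentrality f² × N and 5 numerator degrees of freedom (not stated in the plan, but the value that reproduces its figure), N = 86. Then 86 × 1.10 = 94.6, so 95. Both figures reproduce. Varying the design from 2 to 12 cells leaves N at 86 to 87, so a hospital factor has almost no cost in sample size.

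**2. Chance imbalance by hospital.** N = 95 is from the plan. Simple 1:1 allocation and the share p at one hospital are assumptions. The SD of the between-arm difference in hospital share is √(4p(1−p)/95). The last two columns multiply by an assumed 30-minute difference in PACU time between hospitals.

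| p | SD | 1.96 × SD | 30 min × SD | 30 min × 1.96 × SD |
|---|---|---|---|---|
| 0.2 | 0.082 | 0.161 | 2.5 min | 4.8 min |
| 0.3 | 0.094 | 0.184 | 2.8 min | 5.5 min |
| 0.5 | 0.103 | 0.201 | 3.1 min | 6.0 min |

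An exact hypergeometric calculation with arms of 48 and 47 gives nearly the same SDs, and these probabilities:

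| Share at the larger hospital | Difference of 10 points or more | 20 points or more |
|---|---|---|
| 50% | 31% | 4% |
| 70% | 27% | 2.5% |
| 80% | 31% | 1% |
| 90% | 16% | about 0% |

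The shift has mean zero over repeated randomisations. It is extra variance in the estimate, not bias. The plan gives no SD for PACU time, so the loss cannot be put as a fraction of total variance.

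**3. Anesthesiologist.** Suppose the selected group conducts all block cases and a share q of control cases, and its practice differs from that of other attendings by delta. Then bias = delta × (1 − q). The documents give neither q nor delta.

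Take delta as one fentanyl increment, 25-50 mcg in the plan. The bias is 25-50 mcg at q = 0, 12.5-25 mcg at q = 0.5, and 0 at q = 1.

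In SD units, with 43 per arm (86/2), the bias divided by √(2/43) = 0.216 gives the shift in the test statistic. The false-positive rates of a two-sided 0.05 test are:

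| delta | q = 0 | q = 0.5 | q = 1 |
|---|---|---|---|
| 0.2 SD | 15.3% | 7.5% | 5% |
| 0.3 SD | 28.5% | 10.7% | 5% |
| 0.5 SD | 64% | 21% | 5% |

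These rates show what unequal staffing could do. They do not estimate what it will do here.

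**The case against.** A reader might infer that block patients must be looked after throughout by the selected group, so that anesthesiologist and arm are confounded by design. The text does not support that. The restriction covers placing the block. One anesthesiologist could place it before surgery and another conduct the case, or one pool could serve both arms. Skill in placing the block is part of the intervention and is not a confounder.

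Much of the remaining care is also standardised for both arms. The general anesthetic follows a common regimen, and the freedom to depart from it is attached to induction. Fentanyl is the only intraoperative opioid, and increments have a heart-rate or blood-pressure trigger. Nausea is treated in set steps, the first-line recovery opioid is named, and PACU end time has a rule for non-medical delay. No passage says that the block placer directs recovery care or admission, so the route to those outcomes is weaker than the route to intraoperative opioid.

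A reader might also infer that omitting hospital biases the comparison. Under individual randomisation it does not, and it does not inflate the type I error. It would become systematic only if block patients were steered to the hospital where the selected group works, which the documents do not say. Both hospitals belong to one health system, and eligible cases are scheduled under one named surgeon, which may narrow differences between sites.

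These points stand and limit the finding. They do not close it: the plan neither uses hospital nor says that staffing is the same in both arms.

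**Conclusion.** The point holds as an inexpensive improvement with two parts.

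For hospital, the plan gives up precision. The imbalance has an SD of about 8-10 percentage points, with 95% limits of 16-20. That is one SD of about 2.5-3 minutes in PACU time and 95% limits of about 5-6 minutes, resting on assumed 1:1 simple allocation, 20-50% of patients at one hospital and a 30-minute difference between hospitals.

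For anesthesiologist, the plan leaves open a possible confounding that is conditional on unstated staffing. It is zero if one pool covers both arms and grows in proportion to the staffing difference otherwise. It concerns intraoperative opioid first and recovery outcomes only possibly. No operator effect on the primary pain endpoint is shown. The documents do not establish that confounding is present.

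**What to change.** - **Randomisation:** stratify the existing computer program by planned hospital, using permuted blocks of undisclosed size.
- **Analysis:** include hospital as a factor for pain, opioid consumption and PACU time. Use a hospital-stratified test, such as Cochran-Mantel-Haenszel, for admissions and for opioid consumption if it is coded in categories. If PACU time goes to a rank test, use a stratified one. Stratifying without adjusting would leave the between-hospital variance in the standard error.
- **Staffing:** state that attendings for both arms come from the same pool where scheduling allows, and record the attending for every case.
- **Sensitivity analysis:** repeat the opioid and recovery comparisons by attending group. This says little if the selected group has few control cases, which is why the pool rule matters more.

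The cost is one stratum, one model term and one data field, with no material change in N. The pool rule also costs some scheduling flexibility for no-block cases. A stricter rule, fixing the attending before allocation is opened, would require staffing at the clinic visit or later randomisation, so it is not proposed. A shared pool does not remove discretion exercised with the allocation known; it only stops staffing from differing by arm. Stratification and the pool rule must be in place before enrolment. The model term can be added to the analysis plan later, but before the data are seen by arm.

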## Schedule of Events

	BL	Proc	2W	6W	3M
Informed Consent	✓	-	-	-	-
Inclusion/Exclusion	✓	-	-	-	-
Surgical Details	-	✓	-	-	-
Physical Exam-ROM	✓	-	✓	✓	✓
Visual Analogue Scale (VAS)	✓	-	✓	✓	✓
Adverse Event Assessment	-	✓	✓	✓	✓

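### The primary pain analysis has no defined early score and no named deciding test, so the primary result can be chosen after the data are seen

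*Combined protocol and SAP*

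**What the plan says.** **Time points.** The Statistical Analysis item gives "four dedicated follow up points beyond baseline: a) perioperative (1 to 5 days), b) 2 weeks, c) 6 weeks, and d) 3 months". In the Schedule of Events, VAS is ticked at baseline, 2 weeks, 6 weeks and 3 months. The procedure column has a dash for VAS, and there is no column for days 1 to 5.

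**Collection.** Under Study procedure, "Pain scores will be recorded initially upon arrival to the PACU and thereafter until the patient is discharged from the PACU". Patients then return "at 2 weeks, 6 weeks, and 3 months post-operatively. Pain scores will be evaluated at this time". No other pain score is described.

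**Endpoint and test.** The primary endpoint is the difference in pain between block and no block, with no time point, scale or summary. For the analysis, "The primary outcome measure (pain) will be analyzed using a fixed effects, special, main and interactions, analysis of variance testing (ANOVA". The significance rule is "A p value of 0.05 will be considered statistically significant for all findings", and the missing-data rule is "Intention to treat and last value carried forward will be integrated for all analyses".

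**Sample size.** The calculation assumes a "large clinical effect size (>.40) seen at 5 follow up points for the primary outcome measure of pain" and arrives at 86 subjects, raised to 95 for loss to follow-up.

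**The concern.** Two definitions are missing from the primary analysis.

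The first is the early score. Enrolment is limited to outpatient surgery, so PACU scores normally fall on day 0, outside a window of days 1 to 5. They are probably what the perioperative point means, but the plan does not say so. Nor does it say whether the first, worst, mean or last score counts. Those are different endpoints. The Introduction gives pain immediately after surgery and beyond as the motive for the trial, so the early score matters.

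The second is the deciding test. An arm-by-time ANOVA yields at least two tests of the block: the arm main effect (average difference over time) and the arm-by-time interaction (change in the difference over time). They answer different questions. With 0.05 applied to each and no rule for choosing, two analysts could follow the plan and reach opposite primary conclusions. The role of baseline, as a covariate or as a level of time, is also open and changes both tests.

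The data analyst is blinded, but p-values can be compared across terms or PACU summaries without knowing which arm is which.

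**Working it through.** **1. The plan's own figure.** Read .40 as Cohen's f, with noncentrality λ = f²N, alpha 0.05 and power 0.80. Numerator degrees of freedom (df) are not stated. Of 1 to 10 tried, only 5 gives N = 86 (with 2 to 6 cells; 87 with 8 to 12). Inflation: 86 × 1.10 = 94.6, so 95. The figures can therefore be reproduced.

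They do not reveal the deciding term. In two arms, the main effect has df 1, and the interaction has df 3 (four points) or 4 (five points). Required N at f = 0.40 would be 52, 73 and 80 respectively. An interaction over six time levels, such as five follow-ups plus baseline, would have df (2−1)(6−1) = 5, but no section lists six.

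**2. Assumptions for the illustrations.** 86 split as 43 per arm (allocation ratio not stated), unit SD, equal correlation ρ of 0.3 or 0.5 between a patient's scores, and m time points. The documents give none of these.

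**3. False positives if either term may count.**

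- *Within-patient error term.* The two tests are nearly independent, so the rate is close to 1 − 0.95² = 9.75%. Simulation with 20,000 runs per setting gives 9.5 to 10.2% for four and five points.
- *Fixed-effects ANOVA, rows treated as independent.* The plan names no patient term. The main-effect F is then inflated by about 1 + (m−1)ρ, and its error rate is about P(|Z| > 1.96/√inflation). Simulated rates:

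| Points | ρ | Inflation | Main effect, approximate | Main effect, simulated | Either term, simulated |
|---|---|---|---|---|---|
| 4 | 0.3 | 1.9 | 15.5% | 15.5% | 16.5% |
| 4 | 0.5 | 2.5 | 21.5% | 21.7% | 21.8% |
| 5 | 0.3 | 2.2 | 18.6% | 18.9% | 19.7% |
| 5 | 0.5 | 3.0 | 25.8% | 25.4% | 25.4% |

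**4. Power by deciding term (within-patient error term, four points, baseline not a level).** Let d_j be the difference at point j and d̄ its mean.

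- Main effect: λ = (43/2) d̄² / [(1+(m−1)ρ)/m], df 1 and 84.
- Interaction: λ = (43/2) Σ(d_j−d̄)² / (1−ρ), df 3 and 252.

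*Early-only 0.8 SD.* d̄ = 0.2. Main λ = 21.5 × 0.04/0.475 = 1.81 (ρ 0.3) or 21.5 × 0.04/0.625 = 1.38 (ρ 0.5). Sum of squares = 0.36 + 3 × 0.04 = 0.48, so interaction λ = 21.5 × 0.48/0.7 = 14.7 or 21.5 × 0.48/0.5 = 20.6.

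*Constant 0.5 SD.* Main λ = 21.5 × 0.25/0.475 = 11.3 or 21.5 × 0.25/0.625 = 8.6. Interaction λ = 0.

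| Profile | Main effect | Interaction |
|---|---|---|
| Early-only 0.8 SD | 21–27% | 91–98% |
| Constant 0.5 SD | 83–91% | 5% |
| 0.8 SD at all four points | over 99% | 5% |

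With baseline as a fifth, zero-difference level, constant 0.5 SD gives 66–79% for the main effect and 47–63% for the interaction. For 0.8 SD at all four post-operative points, d̄ = 0.64 and main λ = 21.5 × 0.4096/0.44 = 20.0 or 21.5 × 0.4096/0.60 = 14.7, so main-effect power is 97–99%.

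**5. Single early contrast.** 43 per arm has 80% power for 0.61 SD and 96% for 0.8 SD.

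**The case against.** The best defence is that perioperative plainly means the PACU, that early pain is recorded there, and that a sponsor who expects benefit at every point loses little by leaving the term open. Much of this stands. Three stronger conclusions that a reader might draw are not supported.

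- *That the trial has no early pain data.* PACU scores are required from arrival to discharge. What is missing is their link to the analysis, their scale and their summary.
- *That the trial is underpowered.* The low main-effect figures come from profiles chosen for illustration. The Sample size item may intend the effect at all points, and main-effect power is then 97% or more at 0.8 SD.
- *That last value carried forward will replace early pain with the pre-operative score for everyone.* That would mean ignoring recorded PACU scores. The rule ordinarily fills individual gaps, so this case is remote and needs only a minor safeguard.

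The five-against-four discrepancy is not a proven error in the sample size either. Counting baseline would reconcile the two numbers, but the documents do not say that this was done.

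The defence leaves the main point untouched. Even if the PACU is meant, the summary, the deciding term and the role of baseline are all open, and analyst blinding does not close them.

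**Conclusion.** The point holds and should be fixed before analysis. That the early point lacks a defined score and that no deciding term is named both follow from the text alone. The error rates do rest on assumptions (43 per arm, correlation 0.3 to 0.5, four or five points): about 10% with a within-patient error term and about 17 to 25% with rows treated as independent, against a nominal 5%. The power figures show only that the choice of term can decide the result; they are not estimates for this trial. The open definition of the early point and the missing deciding test carry the weight. Carry-forward and the count of five points are lesser clarifications.

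**What to change.** 1. **Define the early point.** Reconcile the Schedule of Events, the Study procedure text and the Statistical Analysis item. Either use the PACU pain already recorded, with one pre-specified summary on a named scale, and show it in the procedure column. Or, if a day 1 to 5 score is intended, add its collection to the schedule. The summary is the sponsor's choice; the arrival score is one option, because its timing is fixed.
2. **Name one primary test** before any post-operative pain data are analysed, blinded or not: the early between-arm contrast or one stated ANOVA term. Make all other terms and contrasts secondary. State whether baseline is a covariate or a level of time, and that repeated scores use a within-patient error term (repeated-measures or mixed model).
3. **Limit carry-forward.** State that it does not fill a missing early score from the pre-operative baseline.
4. **Explain the count.** State in the Sample size item which five points were counted, and reconcile them with the four in the Statistical Analysis item.

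**Cost.** Mostly wording, and perhaps one added pain score. The sponsor gives up the freedom to choose the primary result later, and the terms or visits not chosen become secondary. The early contrast needs no extra patients if 0.61 SD is an acceptable detectable difference at 80% power. If an ANOVA term is chosen, all visits stay in the primary test, but its power depends on how the effect changes over time.
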